4.2 Exclusion Criteria

- Under the age of 15 years
- Over 29 years of age
- Does not speak or read English
- Assigned female at birth
- Reports 0 episodes of anal intercourse in the past 6 months
- Currently incarcerated
- Planning to move out of the United States in next 12 months
- Does not reside in the United States
- Does not have a smartphone
- If HIV-positive and reports a hemophilia diagnosis or current use of anti-coagulation medication

4.3 Recruitment

We will reach the population using social media ads on sites including Facebook, Tumblr, Instagram, BGC Live, Jack'd, Grindr, Scruff, and other comparable social media platforms (see example copy and images in "Recruitment materials.docx"). Final platforms and materials will be developed alongside our YAB. Social media platforms allow us to specify our audience based on socio-demographic characteristics (e.g., age, race/ethnicity) to increase their specificity to our population. Ads will link interested individuals to a Qualtrics screener where they may verify their eligibility, email the team, or locate a toll-free number if they want to talk to a team member about the study. Via co-I [name], we have access to an online registry with over 1,000 U.S. men, many of whom are HIV-positive, who have expressed interest in participating in other HIV-related studies. We will collaborate with online groups (e.g., Young Black Gay Men's Leadership Initiative; Trans Women of Color Collective) and other advocacy groups to post study and recruitment information. We foresee recruiting 25-30 participants per month during Years 2-4; this staggered design will allow us to accommodate the enrollment and testing of YBLMT in the trial and also allow time for the social networks to develop.

4.4 Informed Consent

Informed consent/assent. Individuals interested in screening for study participation will be consented/assented for screening after reading information about the study and screening procedures. Those who consent to take the screener survey will answer questions to determine their eligibility. Those who do not consent to take the screener will be routed to a public site (e.g., Google). Individuals who complete the screener but are initially ineligible will be asked if they would like provide their first name and email address to be contacted about other research studies in the future, then will be routed to a public site (e.g., Google). For those who are initially eligible based on their screener responses, we will confirm they are eligible by our HIV status quotas. If ineligible by HIV status, we will send an email to inform them. If eligible by HIV status, we will

email each person a unique link to the study's informed consent form. The consent/assent form describes all study procedures, including confidentiality and privacy, information about potential risks, discomforts, benefits of participation, and information regarding who they can contact with further questions. It also states that participation is voluntary, that participants may decide to not take part or to withdraw from the study at any time without penalty or loss of any benefit to which they might otherwise be entitled, and that study participation is in no way related to being able to access care or services.

Waiver of parental consent. We will request that the U. Penn IRB as the central IRB (IRB of Record) grant a waiver of parental consent to participate in this research study for youth participants who are 15 to 17 years of age. The research team has been granted waivers of parental permission for prior studies with sexual minority youth. Under 45 CFR 46.408 (c), an IRB has the authority to waive parental permission if it determines that "a research protocol is designed for conditions or a subject population for which parental or guardian permission is not a reasonable requirement to protect the subjects" and "an appropriate mechanism for protecting the children who will participate as research subjects is substituted" and "that the waiver is not inconsistent with Federal, State, or local law." A waiver of parental permission for studies with lesbian, gay, bisexual, transgender, and queer (LGBTQ) youth that do not involve greater than minimal risk is a common practice among researchers working in the area of gay and lesbian health/mental health. This is done to avoid the selection biases operating in only recruiting youth whose parents are both aware of and comfortable with their sexual orientation. Commonly these youth have explored their sexual orientation without their parents' knowledge as the youth struggle with issues of disclosure and its consequences within the social, religious, and economic context of their families. A requirement for parental permission in this type of study could not only affect a person's willingness to participate, but could also potentially impact the ability of researchers to engage in this type of research with sexual minority youth. Additionally, minors can often seek sexually transmitted infection (STI) and HIV prevention services without parental/legal guardian permission, depending on each site's state laws.

If the purpose of requiring parental permission as stated in CFR is to protect the minor subject, then requiring parental permission for youth in these circumstances is not a reasonable requirement. Additional privacy protections are provided in that all assessments, notes, reports, and other records will be identified by only a coded number to maintain participant confidentiality. These records and any forms that do contain identifying information will be kept in a locked, limited access area (such as a locked file cabinet) at the participating site.

4.5 Screening

As part of app development, we will create a web-based research dashboard for use with the HMP app. We will use a secure (256-bit), HIPAA-compliant dashboard for app content, participant information, and participant app data. Individuals who consent to take the screener survey will be asked to provide their first name, email address, and phone number, then to answer questions to determine their eligibility. Those who do not consent to take the screener will be routed to a public site (e.g., Google). All individuals who complete the screener will be asked if they would like to be contacted about other research studies in the future, then will be routed to a public site (e.g., Google). For those who are initially eligible based on their screener responses, we will then confirm they are eligible by our HIV status quotas. If ineligible by HIV status, we will send an email to inform them. If eligible by HIV status, we will email them a unique link to the study's informed consent form. Consented participants will complete a 30- to 50-minute baseline survey.

Compared to the gold standard (in-person interviewing), a limitation of online research – like mail and phone surveys – is the challenge of verifying a respondent's authenticity. Using best practices "HMP SOP-Applicant Verification.docx") we will attentively reduce the likelihood of duplicative entries, bots, and/or catfishing (fake online personas). Verified participants will be allocated to the study arms using our HIV-stratified randomization procedure.

Web-based recruitment screener: The online survey is hosted by Qualtrics, which will include the eligibility script, consent/assent to be screened, and the screener questions. For those who meet eligibility criteria, we will ask for the first name, email, and phone number of the participant. We use Secure Socket Layer (SSL) encryption for online transfers of information, and data will be stored on Qualtrics' secure, HIPAA-compliant servers.

5.0 STUDY PROCEDURES

5.1 Enrollment Procedures

We will enroll a total of 750 participants. Of these participants, 300 will be HIV-negative and 450 will be HIV-positive. After participants are consented, participants will complete a baseline CASI survey and then will be randomized into the Tailored Information-Only Control (Attention Control), Researcher-Created HMP Network (Intervention Arm 1), or HMP with Peer-Referral Network (Intervention Arm 2). Intervention Arm 2 will only have 150 HIV-positive participants randomized to it, as the remaining participants will be peers who are referred by their peers and enroll if eligible. Upon enrollment, all participants will be provided a link to access the HMP app through the Apple App Store or the Google Play Store for Android. Once downloaded, participants will create their app account by entering their email address, creating a username, password, and PIN, entering their mailing address, opting in or out of notifications, and selecting an avatar.

Those randomized in the Tailored Information-Only Control (Attention Control) will be given a streamlined version of the app. They will have access to the Care Locator and Knowledge Center articles and be able to message the Care Navigator. HIV-negative and sero-unknown participants will be able to request HIV home test kits. HIV-positive participants will be sent HemaSpot devices at Baseline, 6 months, and 12 months. They will not have access to the interactive forums, activities, or the Ask and Expert feature.

Those randomized in the Researcher-Created HMP Network (Intervention Arm 1) will have access to the full HMP app, including access to the Arm 1 Forum in which participants will be able to create threads and comment on any threads in the forum, whether moderator- or usergenerated.

Those randomized to the Peer-Referral Network (Intervention Arm 2) will have access to the full HMP app, including access to the Arm 2 Forum in which participants will be able to create threads and comment on any threads in the forum, whether moderator- or user-generated. The only difference between this version and the Intervention Arm 1, is that two thirds of the users (300) that comprise this group are added by peer referral by the 150 participants who were randomized into this arm.

Intervention Arms 1 (Researcher-generated) and 2 (Peer Referred) will operate as two distinct virtual communities. Participants will not be able to communicate across arms and will only be able to view the posts of participants in their Arm.

5.2 Locator/Contact Information

Once a participant has been consented, enrolled, and downloaded the study app, they will be asked to provide a phone number in addition to their email address where they can be reached. Participants will also be asked to provide their mailing address so we can send their HIV test kit or HemaSpot device to them. Study staff will not send mail unless the participant has confirmed their mailing address and is aware they will be receiving a package. The app will assure participants that HIV test kit and HemaSpot packaging does not reveal their participation in a research study. Additionally, the app will tell participants that all email and text message correspondence will not include any protected health information or information related to study participation.

5.3 Randomization Procedures

Research-team recruited participants will be allocated to the 3 arms using a computer-generated blocked randomization, with stratification by HIV status. For that purpose, randomly permuted blocks of sizes 3 and 6 will be used in order to maintain the integrity of the randomization process. Participants recruited into Intervention Arm 2 through peer-referral will not be randomized as the social network component requires these participants to remain clustered with their nominator.

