2.0 STUDY OBJECTIVES

2.1 Primary Objective:

The primary outcome is successful engagement in care, defined as consistent viral suppression for HIV-positive participants and routine testing for HIV-negative participants.

2.2 Secondary Objective:

A secondary objective is whether user engagement, as measured by both quantitative and qualitative paradata, mediates the intervention effects observed in stigma and HIV care outcomes.

An additional secondary outcome is how changes in intersectional stigma and improvements across the HIV care continuum vary between the researcher-driven vs. peer-referred social network intervention conditions.

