3.2 Sample Size

Participants self-reporting as HIV positive at baseline will be randomized across the three arms (N=150 per arm). Participants who self-report being HIV negative or serostatus unknown at baseline will be randomized (N=150 per arm) into either the Information-Only Control (Attention-Control) or the Researcher-Created HMP Network (Intervention Arm 1). Given that we are allowing the 150 HIV-positive participants assigned to the Peer-Referral version of HMP (Intervention Arm 2) to invite two peers into their social network, we do not know the baseline HIV prevalence among recruited peers. To avoid a priori assumptions of who will be invited, we estimate that half will be HIV-negative or sero-unknown.

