5.4 Intervention/Investigation Procedures

5.4.1. Randomized Trial Design

We will test whether a smartphone application (app) intervention (HMP Stigma) that promotes user-generated content and engagement to address intersectional stigma is associated with *successful engagement in care* as compared to an information-only control arm consisting of online informational articles and resources curated for YBLMT (Specific Aim 1). We will then examine how user engagement mediates the changes observed in stigma and HIV care outcomes across the 12-month follow-up period (Specific Aim 2). To describe how the social network composition of HMP Stigma affects user engagement and our HIV prevention and care outcomes across a 12-month follow-up period (Specific Aim 3), we will allow the composition of the intervention networks to vary. Participants randomized to Intervention Arm 1 will engage in a researcher-created network where half of the participants are HIV-positive. Participants randomized to Intervention Arm 2 will engage in a peer-referred network in which they may invite 2 peers (irrespective of race/ethnicity and/or HIV status) into the study. All participants who are randomized into Arm 2 will be HIV positive and we assume that peers they refer will be a mix of HIV-negative, HIV-positive, and HIV-unknown status.

5.4.2 HemaSpot Package, Delivery and Tracking: 120

At baseline and months 6 and 12, HIV-positive participants will be mailed a HemaSpot package which contains: 1) one HemaSpot kit with all necessary materials to perform a finger prick, a biohazard bag, and study labels; 2) an instructional booklet for how to properly collect a specimen for the HemaSpot device; 3) a return envelope addressed to the processing lab with pre-paid postage; and 4) a lab sheet which includes the participant's study ID. The U. Penn team will

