10.2 Power Estimates

The primary outcome for the proposed trial is stratified by HIV status and defined as *successful* engagement in care. For HIV-positive participants at baseline, we define successful engagement in HIV care as consistent VS across the 12-month trial (per IOM guidelines²¹⁸). For HIV-negative

or sero-unknown at baseline, we define successful engagement in care as participation in routine HIV testing (2 HIV tests with at least 3 months apart from one another, per CDC guidelines²¹⁹). We define power as correctly identifying the difference in the proportions of YBLMT with serospecific engagement in HIV care within 12 months of each intervention arm (2 arms: HMP Stigma with researcher-created network, HMP Stigma with peer-referred network) to the control arm (Information Control), thus powering for 3 independent hypothesis tests. Our sample size calculations are based on pair-wise HIV-stratified comparisons of the 3 groups in terms of proportion of successful engagement using a two-sided significance level of 0.05 altered by the number of comparisons using a Bonferroni adjustment (significance level is 0.017 for 3 comparisons). To have 80% power to detect a minimum effect size (OR=1.9) of successful engagement in care between the 3-arm trial, we will require at least 450 HIV-negative and 450 HIV-positive participants to detect a 17% difference in successful engagement in. In the event of a 20% loss to follow-up, we will have sufficient power to detect an OR=2.1 (18% difference) at alpha=.017. Participants may continue the study even if they miss an assessment intermittently. We will compare those who completed different follow-up interviews with those who did not on key baseline predictors to check for possible sampling bias. Our analysis will use ITT as appropriate.

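### In the HIV-negative/unknown stratum, the primary comparison of the peer-referral arm with Control is non-randomised and unadjusted

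*Combined protocol and SAP*

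**What the plan says.** **Allocation.** Section 3.2 says that HIV-negative or unknown-status recruits "will be randomized (N=150 per arm) into either the Information-Only Control (Attention-Control) or the Researcher-Created HMP Network" (Arm 1). Section 5.4.1 adds: "All participants who are randomized into Arm 2 will be HIV positive". Section 5.1 agrees: "Intervention Arm 2 will only have 150 HIV-positive participants randomized to it". It gives the makeup of the 750 directly enrolled participants as follows: "Of these participants, 300 will be HIV-negative and 450 will be HIV-positive".

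**Peers.** Arm 2's remaining members, about 300, are invited by the 150 randomised participants, up to two each. Section 5.3 states: "Participants recruited into Intervention Arm 2 through peer-referral will not be randomized", and gives the reason that they must stay clustered with their nominator. On their HIV status, section 3.2 says only "we estimate that half will be HIV-negative or sero-unknown". Section 4.1 admits peers of any race or ethnicity, whereas all other participants must identify as Black and/or Latino.

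**Analysis.** Section 10.2 plans three pairwise comparisons within HIV status at 0.017 and says "we will require at least 450 HIV-negative and 450 HIV-positive participants". Section 10.3.1 fits logistic regressions stratified by serostatus with group as the only term. It compares each active arm with Control, and adds that the two intervention arms can be compared as well.

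**Objectives.** Section 2.2 lists the comparison of the two networks as secondary: "An additional secondary outcome is how changes in intersectional stigma and improvements across the HIV care continuum vary between the researcher-driven vs. peer-referred" networks.

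**The concern.** A regression on group alone estimates an intervention effect when randomisation has made the groups comparable. That does not apply to the HIV-negative part of Arm 2. Its members were picked by an HIV-positive participant who earns a payment for each enrolled peer (section 3.3.2), and they meet a wider race/ethnicity criterion. The Control members they are compared with came through study-team recruitment and were randomised. A difference in routine HIV testing could therefore reflect who was referred as well as what the app did, and the primary model contains nothing to separate the two.

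At stake is the Aim 1 claim for peer referral among HIV-negative participants. Followed as written, the plan would report an observational contrast as a randomised efficacy result, at a significance level whose error guarantee presumes comparable groups.

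**Working it through.** **1. Where the 450 HIV-negative participants come from**

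| Group | HIV-negative/unknown | Route | Source |
|---|---|---|---|
| Control | 150 | randomised | 3.2 |
| Arm 1 | 150 | randomised | 3.2 |
| Arm 2 | about 300 × 0.5 = 150 | referred, not randomised | 3.2, 5.1, 5.3 |

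150 + 150 = 300 matches section 5.1. 300 + 150 = 450 reproduces the section 10.2 figure, but only by counting peers. Without them, Arm 2 has no HIV-negative group. The 150 is the protocol's estimate, not a fixed number.

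**2. Which contrasts are affected**

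| Contrast | HIV-negative/unknown | HIV-positive |
|---|---|---|
| Arm 1 v Control | randomised | randomised |
| Arm 2 v Control | **not randomised** | randomised if peers are excluded |
| Arm 2 v Arm 1 | **not randomised** | randomised if peers are excluded |

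The documents do not say whether the other 150 or so peers, assumed HIV-positive, enter the HIV-positive comparison. If they do, that stratum has about 450 + 150 = 600 members and its Arm 2 contrasts have the same problem.

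**3. Illustration of the effect on false positives**

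The documents give no difference between peers and recruits, so the gaps below are assumed. Test: two-sided two-proportion z-test with pooled null variance, alpha 0.017 (z = 2.387), no app effect, rates 0.5 ± g/2.

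Rejection probability = Φ((g − z·s0)/s1) + Φ((−g − z·s0)/s1), with s0 = √(2·0.5·0.5/n) and s1 = √((p1(1−p1) + p2(1−p2))/n).

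For n = 150 and g = 0.10: s0 = 0.0577, s1 = 0.0575; (0.10 − 2.387 × 0.0577)/0.0575 = −0.66, so the probability is about 0.255.

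| Assumed gap | 150 v 150 | 120 v 120 (20% loss) |
|---|---|---|
| 0 | 1.7% | 1.7% |
| 2 points | 2.4% | 2.2% |
| 5 points | 6.4% | 5.4% |
| 10 points | 25.5% | 20.0% |

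These figures ignore clustering. If all 150 peers came as pairs sharing a nominator, the design effect would be 1 + ICC. With an assumed ICC of 0.05 to 0.3, the 150 would count as about 143 to 115.

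**4. Power of the one randomised HIV-negative contrast (Control v Arm 1, 150 v 150)**

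Section 10.2's alpha reproduces: 0.05/3 = 0.0167. Its two effect sizes do not fit together. The largest risk difference that an odds ratio of 1.9 can give is (√1.9 − 1)/(√1.9 + 1) = 0.378/2.378 = 0.159, or 15.9 points, not 17. Both targets are therefore shown. The control rate is not given; the 17-point range covers assumed rates of 20% to 70%.

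| Alpha | Family | OR 1.9, maximum power | 17 points |
|---|---|---|---|
| 0.0125 | 0.05/4: four randomised contrasts trial-wide | 60% | 67–87% |
| 0.017 | 0.05/3: Arm 2 v Arm 1 made secondary | 65% | 71–89% |
| 0.05 | one contrast in its own stratum | 79% | 84–95% |

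The OR 1.9 maxima occur at a control rate of about 42%.

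**5. Randomisation wording**

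Section 5.3 allocates study-recruited participants across three arms, stratified by HIV status, in blocks of 3 and 6. HIV-negative recruits have two arms, and a block of 3 cannot be split equally between two.

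**The case against.** The strongest reply is that nothing is hidden. Section 5.3 says openly that peers are not randomised and why, and section 5.4.1 lets network composition vary on purpose to serve Aim 3. Section 10.3.3 already plans mixed models and a GEE check for care outcomes across the two intervention groups, with network covariates. Section 10.3.1 compares baseline characteristics by group, and section 10.2 promises intention-to-treat analysis where appropriate.

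The disclosure stands: the fault lies in the primary model and its labelling. The rest does not repair Aim 1. The section 10.3.3 models belong to Aim 3 and name no clustering by nominator. Baseline tables can show measured imbalance, but the primary model does not act on it. Intention-to-treat needs a randomised assignment, which peers lack.

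A reader might infer more than the documents support:

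- **That the objectives and the analysis plan flatly contradict each other on Arm 2 versus Arm 1.** Section 2.2 is worded broadly, covering stigma and the care continuum. Section 10.3.1 offers the test as an addition and never calls it primary. Section 10.2 first describes arm-versus-Control comparisons, yet divides alpha by three. The contrast's status is unclear, and no more than that.
- **That the 450 HIV-positive participants in section 10.2 show that HIV-positive peers are excluded.** The figure is a minimum and excludes nobody.
- **That the peers cause the power shortfall.** The shortfall for an odds ratio of 1.9 at 150 per arm is separate, and for 17 points at alpha 0.05 there is none.

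**Conclusion.** The point holds and should be fixed before analysis. By the protocol's own allocation rules, the primary Arm 2 versus Control contrast in the HIV-negative/unknown stratum is non-randomised, and the plan analyses it unadjusted and without allowance for nominator clustering. That is one of four arm-versus-Control contrasts. Arm 2 versus Arm 1 in that stratum shares the defect. The HIV-positive Arm 2 contrasts would share it only if referred peers are counted there.

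This conclusion rests on the text of sections 3.2, 5.1, 5.3, 5.4.1 and 10.3.1 and needs no numerical assumption. The size and direction of any bias are unknown. The false-positive figures depend wholly on the assumed gaps: small at 2 points (2.4% against 1.7%), serious at 10 (about 26%, or 20% at 120 per group). It would be wrong to read the trial as a whole as non-randomised: Control versus Arm 1 is sound in both strata.

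**What to change.** 1. Define the Aim 1 primary set as randomised participants only: the three HIV-positive arms of 150 with peers excluded, and Control versus Arm 1 among the 300 randomised HIV-negative/unknown participants.
2. Report every contrast that uses referred peers as secondary and explicitly non-randomised. Adjust for age, race/ethnicity and the baseline value of the outcome where collected, with GEE or cluster-robust standard errors by nominator; section 10.3.3 already provides a GEE framework. State that adjustment removes only measured confounding.
3. State whether Arm 2 versus Arm 1 is primary or secondary.
4. Restate section 10.2 with 300 randomised HIV-negative/unknown participants and one randomised contrast. Name its alpha and family in advance, settle on one consistent effect size, and recompute power.
5. Reconcile the three arms and block sizes in section 5.3 with the two-arm allocation in section 3.2.

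**Cost.** Analysis-plan text, a recalculated section 10.2 and protocol edits that need IRB review under section 11.3; no new data. The HIV-negative Arm 2 contrasts lose confirmatory status, which the design never supported, and that stratum's one confirmatory test rests on 300 participants.

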Peer-referred HMP Network Arm: Participants randomized to Intervention Arm 2 (peer-referred network) will be enrolled into a parallel (but separate) version of HMP Stigma. The only difference between Arm 1 and Arm 2 is that participants in Arm 2 will have a referral feature in their profile that allows them to earn \$20 in e-gift cards if they successfully refer and enroll 2 peers of their choosing (\$10 per peer) in the first 45 days of their study participation. The referral feature will create a customized link for each participant that can be emailed or text messaged to invite peers into the study. 189 Simple instructions will be provided at enrollment and in the app describing how to refer them. Participants may send referral links until two of their peers have screened eligible and enrolled in the study. Participants may send referrals from Day 1 – 45 of their time in the trial. If two of a participant's referred peers successfully enroll within that time window, at that point, the original participant will receive a notice from the study team that they have successfully reached their referral quota and the referral feature will deactivate. their referral incentives and HMP usernames of their referrals within their profile. While they will be able to see whether their peer has enrolled and what username the peer created, they will not receive any information about any of their peers' survey responses, including those who screened ineligible. Referred peers will see the HMP username of their referrer; they will not be eligible to refer their own peers.

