10.3 Statistical Analysis Plan

10.3.1 Specific Aim 1:

Specific Aim 1 is to test whether a smartphone application (app) intervention (HMP Stigma) that promotes user-generated content and engagement to address intersectional stigma is associated with successful engagement in care as compared to an information-only control arm consisting of online informational articles and resources curated for YBLMT. Clinical and demographic characteristics will be described for the entire sample, and by treatment group. These will be compared between treatment groups using ANOVA or Kruskal-Wallis test for continuous variables, and chi-square tests for categorical variables. We will conduct primary analyses of our successful engagement in care outcome using logistic regression analyses to compare each active treatment group to the control in pairwise comparison tests at an adjusted significance level of 0.017 to reduce Type-I errors in our 3-arm trial. This approach allows us to also test for differential efficacy between the two intervention conditions (i.e., Does peer-referral HMP outperform the researcher-created HMP arm?).

Logistic regression analyses will be stratified by serostatus. The regression will be run with group assignment only in the model. Among HIV-positive participants, we will examine how intervention conditions influence YBLMT's likelihood of consistent VS over 12 months. We will also test intervention effects on retention in care per IOM guidelines (i.e., proportion of HIV-positive participants who obtain at least 2 viral load tests (at least 3 months apart) within 12 months). For HIV-negative YBLMT, we will compare the proportion of participants who obtain at least 2 HIV tests (at least 3 months apart) within 12 months across arms. Estimates will be calculated and presented with corresponding 95% exact binomial confidence intervals. In secondary outcome analyses, we will compare arms across other HIV care continuum outcomes, as well as stigmarelated (e.g., reduction in HIV-related stigma) outcomes, using a logistic regression with group assignment on the model assuming no imbalances due to successful randomization.

10.3.2 Specific Aim 2:

Specific Aim 2 is to explore whether user engagement, as measured by paradata, mediates the intervention effects observed in stigma and HIV care outcomes.

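### The Aim 1 primary test and exact intervals ignore referral groups in Arm 2; test size is modestly inflated among HIV-negative participants, and among HIV-positive participants only if peers are pooled with nominators

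*Combined protocol and SAP*

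**What the plan says.** **How Arm 2 is formed.** Section 3.3.2 rewards each participant randomized to Arm 2 if they "successfully refer and enroll 2 peers of their choosing". Peers cannot refer others, so a referral group holds at most three people. Section 5.3 does not randomize peers, because the network component "requires these participants to remain clustered with their nominator". Section 5.1 makes 300 of the 450 Arm 2 users referred peers. Section 5.4.1 says that everyone randomized to Arm 2 is HIV-positive, and section 3.2 expects half of the peers to be HIV-negative or of unknown status.

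**How Arm 2 is analysed.** Section 10.3.1 compares arms pairwise by logistic regression within serostatus: "The regression will be run with group assignment only in the model". Estimates are "presented with corresponding 95% exact binomial confidence intervals". Section 10.2 sets the level "using a two-sided significance level of 0.05 altered by the number of comparisons", and states that the "significance level is 0.017 for 3 comparisons". It uses no ICC or design effect.

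**Where correlation is handled.** Mixed models, a term for peers' outcomes and an exchangeable GEE appear in section 10.3.3, under Aim 3. Random effects are left to exploratory work there, and nothing carries these methods over to the Aim 1 test.

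**The concern.** Ordinary logistic regression and the exact binomial interval both take each person's outcome as independent of everyone else's. A nominator and two chosen friends may well resemble each other in testing or care. The protocol does not measure this, but its Aim 3 model allows for it by including peers' outcomes. With positive correlation, the Arm 2 proportion varies more than the model-based standard error says, and contrasts with Arm 2 reject too often under the null.

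The Control arm and Arm 1 contain no referral groups, so Arm 1 versus Control is untouched by this. At stake are the per-comparison level that the plan set to limit false positives, and the stated 95% coverage for Arm 2.

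**Working it through.** **Inputs from the documents**
- Level: 0.05/3 = 0.0167, stated as 0.017, two-sided. This reproduces. The critical value is z = 2.387.
- HIV-negative stratum: 150 in Control (section 3.2); about 150 in Arm 2, all of them peers (half of 300).
- HIV-positive stratum: 150 in Control; Arm 2 has 150 randomized nominators, or about 300 people if the 150 or so HIV-positive peers are added.

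**The plan's sample size.** Section 10.2 states "To have 80% power to detect a minimum effect size (OR=1.9) of successful engagement in care", with "450 HIV-negative and 450 HIV-positive participants to detect a 17% difference". This did not reproduce. An OR of 1.9 allows at most a 15.9-point difference. For 17 points centred on one half (0.415 v 0.585, OR 1.99), a two-sided 0.017 test needs 179 per arm, and 150 per arm gives 71.4% power. That is a separate matter and does not bear on the argument here.

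**Assumed, because the documents do not give it:** ICC from 0.05 to 0.30. I also assume that each nominator enrols two peers and that each peer is HIV-negative with probability 0.5, independently of the other.

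**Design effect:** DEFF = 1 + ICC × (E[m²]/E[m] − 1), where m is the number of group members in the stratum.
- HIV-negative: m is 0, 1 or 2 with probability 0.25, 0.5, 0.25. E[m] = 1 and E[m²] = 1.5, so DEFF = 1 + 0.5 × ICC.
- HIV-negative, all in pairs: DEFF = 1 + ICC.
- HIV-positive, pooled: m is 1, 2 or 3 with probability 0.25, 0.5, 0.25. E[m] = 2 and E[m²] = 4.5, so DEFF = 1 + 1.25 × ICC.
- HIV-positive, randomized only: one person per group, so DEFF = 1.

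**Real size:** 2 × (1 − Φ(2.387/√R)), where R is the true variance of the difference divided by the variance the model assumes. With 150 v 150, R = (1 + DEFF)/2. With 300 v 150, R = (2 + DEFF)/3.

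Example: HIV-negative, ICC 0.30. DEFF = 1.15, R = 1.075, √R = 1.0368, and real size = 0.0213.

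| ICC | HIV-negative, half mix | HIV-negative, all pairs | HIV-positive, pooled | HIV-positive, randomized only |
|---|---|---|---|---|
| 0.05 | 0.0177 | 0.0184 | 0.0182 | 0.0170 |
| 0.10 | 0.0184 | 0.0198 | 0.0194 | 0.0170 |
| 0.20 | 0.0198 | 0.0229 | 0.0218 | 0.0170 |
| 0.30 | 0.0213 | 0.0260 | 0.0244 | 0.0170 |

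A beta-binomial simulation of the Wald logistic test (60,000 runs, true proportion 0.5) agrees: 0.0174 to 0.0214 for HIV-negative with the half mix, and 0.0178 to 0.0231 for HIV-positive pooled, over ICC 0.05 to 0.30.

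**Coverage of the exact 95% interval for the Arm 2 proportion, same simulation**

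| ICC | HIV-negative, half mix | HIV-positive, pooled |
|---|---|---|
| 0 | 95.9% | 95.6% |
| 0.10 | 95.4% | 94.2% |
| 0.20 | 94.9% | 92.9% |
| 0.30 | 94.4% | 91.4% |

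**Power.** For 0.415 v 0.585 in the HIV-negative stratum, power falls from 71.4% to between 70.8% (ICC 0.05) and 67.7% (ICC 0.30). An effective 150 HIV-negative peers would need 150 × DEFF, or 154 to 173 people.

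**The case against.** **The effect is small, and the ICC is assumed.** This stands. Groups hold at most three people and are split by serostatus. The 0.017 level exists to control error over three comparisons, and Bonferroni has some slack. By simulation, the chance of any false positive among the three pairwise tests is about 4.5% without clustering. It becomes about 4.6 to 5.2% for HIV-negative with the half mix, and about 4.7 to 5.7% for HIV-positive pooled, over ICC 0.05 to 0.30. Any breach of 5% is under one percentage point.

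**Section 5.3 uses clustering to explain allocation, and says nothing about outcomes.** This is fair. The section establishes the grouping; correlated outcomes are an inference, though one the Aim 3 model allows for.

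**A reader might infer that every Arm 2 result misses its level.** The documents do not support that. The 450 HIV-positive participants in section 10.2 can be met by randomized participants alone. If they are the analysis set, the HIV-positive comparison holds its level. The documents do not settle whether peers join that set.

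**A reader might infer that the 95% intervals are badly off, at about 90.5 to 93.5% coverage.** That range comes from a normal approximation with the pooled HIV-positive design effects. The exact interval is conservative and starts above 95%, so the real shortfall is smaller; in the HIV-negative stratum it is below one point in this simulation.

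**The fix does not rescue the HIV-negative Arm 2 contrast.** This also stands. Peers are chosen rather than randomized, and each intervention arm, Arm 1 included, shares one forum. A robust variance addresses neither.

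**Conclusion.** The point holds in limited form and should be fixed. In the HIV-negative stratum the specified Aim 1 analysis understates the Arm 2 standard error for any positive within-group correlation. That error is too small by 1.2% to 7.2% at ICC 0.05 to 0.30 with the half mix, which gives a real size of about 0.018 to 0.021; pairing of all HIV-negative peers takes it to about 0.026. In the HIV-positive stratum the conclusion depends on an analysis set that the plan leaves open: about 0.018 to 0.024 with peers pooled, and 0.017 without them. Exact-interval coverage for ICC 0.1 to 0.3 is about 94 to 95% and 91 to 94% respectively. Everything rests on the assumed ICC range and the assumed mix of peers. Arm 1 versus Control is not affected by referral groups.

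**What to change.** In section 10.3.1, state that every contrast and proportion that includes referred peers uses cluster-robust (sandwich) standard errors. The cluster is the nominator's referral group, and everyone else is a cluster of one. For Arm 2, report the matching robust interval in place of the exact binomial one. The same text should say whether HIV-positive peers enter the HIV-positive primary comparison, since that decides whether the correction is needed there.

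The cost is a short addition to the plan. The referral feature in section 3.3.2 already gives each nominator a customized link, so the cluster identifier should be available. Point estimates do not change; Arm 2 intervals become slightly wider and power slightly lower. If the correlation is nil, results are essentially unchanged. The addition should make clear that it corrects only the variance from referral groups. It does not remove selection bias from non-randomized peers or dependence across a shared forum.
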